For any phase of the study, if an individual who is suicidal or homicidal is identified during the screening process or at any time during the study, the study staff interacting with the individual will immediately notify 1) the participant's non-study clinician (if a release of information has been obtained), 2) the site PI, who is a practicing licensed psychiatrist, and 3) if the participant is < 18 years old, their legal guardian, so that all available and appropriate measures may be taken to ensure the prompt safety and most appropriate care setting for the participant. If at any point during the study a patient has active suicidal behavior on the C-SSRS; an increase from baseline in suicidality, as measured by the C-SSRS, or appears to the investigator to pose a risk of self-harm or a harm to others, guardians will be informed and the participant will be referred to appropriate clinical

care. Individuals who are at immediate risk of harm to themselves or others will be taken to the psychiatric emergency department located in close proximity to where the proposed study will be conducted at both sites.

Additionally, participants/legal guardians will be informed during the informed consent/assent process that if the participant/legal guardian experiences any suicidal ideation, intent, or plan (as measured by the C-SSRS or clinical assessment) during a focus group, advisory board meeting, cognitive interview, a CAE-AYA or ETAU session, or a rating scale interview they will be evaluated immediately by a study clinician and referred to the appropriate clinical follow-up. Specifically, if a participant is judged to be a danger to themselves or others, the participant will be taken to the psychiatric emergency department for further evaluation. As described, If the participant is < 18 years old, their legal guardian will be informed of any suicidal or homicidal ideation and of any necessary treatment referrals or further evaluation (e.g., assessment at the psychiatric emergency room).

Provisions to Protect the Privacy Interests of Research Participants

Complete confidentiality cannot be assured due to the nature of group interactions in the focus groups and advisory board, although we will request that participants in these groups maintain other participants' confidentiality. Confidentiality of the research data will be protected in several ways. Paper assessment forms and other study records will be stored in the locked research offices of the site PIs and/or study staff. Participants will be identified by a separate study ID number on all study records. The lists that link study ID codes with participant names, and all electronic study records will be stored on password-protected, encrypted computers or secure servers. Only aggregate data will be presented or published, and will be presented such that individual patients cannot be identified. The proposed project's research personnel who will have access to participant identities are the study PIs, co-investigators, and the study research assistants, interventionists and data analyst. All study personnel will be required to be certified in the protection of human subjects throughout the study. The focus groups, advisory board, and therapy sessions will be recorded and reviewed by study staff for fidelity. The recorded sessions will be stored on a secure server, and will be destroyed at the end of the study, after all data analyses have been completed.

The identifiable information will not be reused or disclosed to any other person or entity outside UHC other than those identified in the protocol, except as required by law, for authorized oversight of this research study, or as specifically approved for use in another study by an IRB.

Potential Benefit to Research Participants

Potential benefits include a thorough psychiatric evaluation performed by study staff with expertise in the diagnosis and treatment of bipolar disorder, and the chance to contribute to a scientific investigation, which may be of benefit to patients with similar illnesses in the future. Participants may also benefit from participating in the sessions and may find it helpful to talk about their conditions and challenges in adherence. There is no guarantee of benefits to any participant. However, the goal of this project to develop a contribution to knowledge, which can be useful in improving the understanding and management of poor adherence in AYA with BD. It will be explained to participants and legal guardians that participation in the study may not benefit them in any way but may be of benefit to other patients in the future. Overall, the risks associated with this study are minimal to the participants and they may receive direct benefit from their study participation as previously described. Therefore, in the opinion of the investigators, the benefits associated with this study outweigh the risks.

Withdrawal of Research Participants

Individuals will be discontinued from the protocol prior to 24 weeks if they wish to withdraw for any reason at any time. Since the intervention is an addition to their regular treatment and does not include medication, there is no need for follow-up with the research team.

Should the need arise to discontinue a patient from the study because of symptom worsening (as defined previously) or for any other reason, including patient/legal guardian withdrawal of consent, we will collaborate with the patient/legal guardian, and their non-study related clinician to determine treatment options for that patient following study discontinuation.

Cost to participants

Participants and their insurance will not be charged for any study visits. Subjects may incur costs such as travel, parking, and meals. These are reasonable costs that a subject will incur as a result of going to study visits. Subjects are compensated for these costs as outlined below.

Research Participant Compensation

Phase 1 focus group and advisory board participants will each receive for \$20 for each meeting they attend.

Phase 2 participants will receive \$30 for each usability session they attend.

Phase 3 RCT participants ages 13-21 will receive \$25 per assessment visit for attending the 5 assessment visits and an additional \$10 at the V3 visit for returning the SimpleMed box. Throughout the CAE-AYA intervention sessions, small token items of insignificant value (e.g., \$5 gift card, pens, notebooks, key tags, lanyards, mini calendars, etc.) may be given and will not be used as a contingency for study participation.

At the UH/CWRU site stipends will be paid by check mailed to the participant's home or in some cases, in cash at the visit if cashing a check would be burdensome on the participant, or via gift card/e-gift card. At the UC site, subjects will be paid in the form of a prepaid debit card or gift card.

Participants in all 3 phases will be offered a bus pass or parking pass for any meetings, sessions, and assessment visits. In some circumstances other transportation (i.e., taxi or Uber/Lyft) will be arranged and the cost will be covered by the study if necessary.

Provisions to Monitor the Data to Ensure the Safety of Research Participants

The study PIs, Drs. [name] and [name], will monitor the study to ensure data integrity and the safety of the participants. The CWRU site Data Coordinator, will review the data for discrepancies on a regular basis and will review the study records for compliance with IRB requirements and verification of source documents. The PIs will hold regular weekly meetings across sites via teleconference with all study staff to review study progress and any issues that may come up regarding data integrity and completeness.

Data and Safety Monitoring Board or Committee

For Phase 3, we are proposing that a DSMB be comprised of experts in the following fields: a behavioral psychiatrist/psychologist, expert in BD, and biostatistician. These experts, from outside the departments of either PI, will review and evaluate the accumulated data for participant safety, adverse events, study conduct and progress every 6 months. The DSMB will make recommendations to the appropriate regulatory agencies (IRB, NIH) concerning continuation, modification or termination of the study. DSMB members will be identified before the start of the clinical trial in Phase 3 of the project.

Alternatives to Participation

The alternative is for research subjects not to participate.

References

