designed to support data capture for research studies. Each site (CWRU and UC) will use their own institutions' REDCap. When the study is over, UC will send their de-identified data to the CWRU site where it will be combined with CWRU data and analyzed as outlined below. Consistent with the developmental nature of the R34 mechanism, we will evaluate feasibility, acceptability and satisfaction of the interventions using the feasibility evaluation noted in section C.3 e. and C.3f., attendance tracking, and an exit interview that includes Likert scales to evaluate perceived benefit vs. burden as well as open-ended/write-in suggestions. Pls at each of the proposed study sites will be responsible for overseeing data input and quality and, working with [name], will oversee the data analytic procedures. For the primary RCT outcome, we will adopt Type I error level of 0.05. Multiple comparisons adjustment will be applied for barrier variable analyses. We propose to enroll 40 AYAs with BD who are randomized to either CAE-AYA (N=20) or to ETAU (N=20). Based on our prior studies,^{28, 29} we expect up to 30% of participants will discontinue study participation during the 24-week study period.

As outlined in Aim 2, the primary statistical outcome measure will be change in adherence behavior as measured by past month TRQ. Adherence rates will be calculated for TRQ as well as the SimpleMed as follows: the number of days with a missed dose will be divided by the number of days in the time period and then multiplied by 100 with higher number indicating worse adherence.

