In Aim 3, it is hypothesized that reductions in adherence barriers (e.g. BD knowledge, medication routines, communication with clinicians and parents/guardians, and substance use/risk behaviors) will be associated with changes in adherence. We will regress respective changes in adherence levels upon changes in barrier variable values. We will also compare difference values in barriers by treatment arm, and include treatment indicator variables in regression models. Modeling assumptions will be thoroughly assessed, and transformations will be considered. In a similar manner, we will also examine whether improvements in adherence behaviors correlate with improvements in symptoms and HRQoL. These analyses will support the clinical interpretability of effect sizes in adherence change for future studies. Barrier variables with change values that appear to be associated with change in adherence levels and that appear to differ by treatment will be considered further as mediator variables, following as in MacKinnon (2008)⁸³ and Preacher and Hayes (2008).⁸⁴ This will involve single mediator analyses as well as exploring multiple mediator models. These analyses will involve the treatment variable and change in adherence values. Associated standard errors of estimated indirect effects will be derived through bootstrapping, using the M-Plus software.

Missing Data:

Data that remain missing despite our retention efforts will be accommodated in our analyses and their impact evaluated through sensitivity analyses. The models we propose can be estimated without bias under the missing at random (MAR) assumption⁸⁵ and provide valid analysis as long as auxiliary covariates associated with missingness (if any) are included in the analysis model. To assess which covariates may be associated with missing outcome data, we will create binary indicators of whether the outcome was missing (=1) or not (=0). If a covariate is correlated with missingness at r >0.40 and is correlated at r >0.40 with the original response variable, it will be included in the analysis as an auxiliary correlate.⁸⁶ We will conduct preliminary assessment of the missing at random (MAR) assumption by pattern mixture models that relax the missing at random assumption. We will also consider selection models to assess sensitivity to MAR in a Bayesian Markov Chain Monte Carlo framework,⁸⁷.

Power:

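### Aim 3 screens mediators on both paths and then estimates the indirect effect in the same 28 to 40 patients, so the indirect effects it reports are biased away from zero

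*Combined protocol and SAP*

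**What the plan says.** The Aim 3 paragraph of the Data Analysis section works in two stages.

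- **First stage.** Change in adherence is regressed on change in each barrier, barrier change is compared between arms, and treatment indicators enter the regressions.
- **Second stage.** This is restricted: barriers whose change looks linked to adherence change and "that appear to differ by treatment will be considered further as mediator variables", in single-mediator and then multiple-mediator models. "Associated standard errors of estimated indirect effects will be derived through bootstrapping".

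The plan gives no numerical meaning for *appear*. It describes no hold-out sample, shrinkage or selection-adjusted interval, and does not say whether the bootstrap repeats the screen.

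Other relevant statements:

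- The trial randomises 40 participants, 20 per arm, and "we expect up to 30% of participants will discontinue study participation during the 24-week study period".
- Earlier in Data Analysis: "Multiple comparisons adjustment will be applied for barrier variable analyses". The method is not named.
- Project Design labels Aim 3 exploratory. Hypothesis 3 nevertheless predicts mediation through knowledge, communication with clinicians and with parents or care partners, medication routines, and substance use or risk-taking.

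**The concern.** In a single-mediator model the indirect effect is a × b, where a is the effect of treatment on the barrier and b is the association of the barrier with adherence given treatment. The screen keeps a barrier only when the sample estimates of both look large enough. In a sample this small, a barrier often passes because chance pushed one or both estimates up. Multiplying those same estimates carries the chance component into the reported effect. A bootstrap run on the survivors describes sampling variation around the selected value and leaves that value where it is.

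Two things are at stake. The mechanism results of this pilot would look stronger than they are. In addition, a domain named in Hypothesis 3 could end the trial with no indirect effect at all, because it missed a screen that nobody can reproduce.

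**Working it through.** **Inputs from the documents.** N = 40, 1:1. Attrition up to 30%, so 40 × 0.70 = 28 completers, 14 per arm. Two-sided alpha 0.05. The Power section gives reference effects at power 0.70 of d = 0.975 (t-test) and r = 0.438 (correlation).

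**Step 1: reproduce the plan's figures.** For the two-sample t-test, the noncentrality is d√(n/4) = 0.975 × √7 = 2.58 with 26 df, which gives power 0.70. For the correlation, the fixed-predictor form has noncentrality r√n/√(1−r²) = 0.438 × 5.292/0.899 = 2.58 with 26 df, which also gives power 0.70. Both stated figures are reproduced, so n = 28 is the sample the plan had in mind.

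**Step 2: assumptions the plan does not supply.** These are a screening threshold and the true path sizes. I take thresholds of p<0.05, p<0.20 (a loose reading of *appear*) and p<0.05/6 = 0.0083 (a Bonferroni reading of the promised adjustment over six scales). For path sizes I take the plan's reference effects and a small pair, d = 0.3 with partial correlation ρ = 0.3.

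**Step 3: simulate the rule.** M = d·T + e₁ and Y = b·M + e₂, with standard normal errors, no direct effect, one mediator at a time and b = ρ/√(1−ρ²). The true indirect effect is d·b:

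- reference effects: 0.975 × 0.438/0.899 = 0.475
- small paths: 0.3 × 0.3/0.954 = 0.094

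A trial passes if both the a-path and the treatment-adjusted b-path meet the threshold. Inflation is the mean of the estimated a·b among passing trials, divided by the truth (200,000 trials per cell).

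| Screen on each path | Reference, n=28 | Reference, n=40 | Small, n=28 | Small, n=40 |
|---|---|---|---|---|
| none | 1.00 | 1.00 | 1.00 | 1.00 |
| p<0.20 | 1.2 | 1.07 | 3.0 | 2.4 |
| p<0.05 | 1.47 | 1.21 | 5.1 | 3.7 |
| p<0.05/6 | 1.9 | 1.47 | about 8 | 5.6 |

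At p<0.05 the share of trials passing is 44%, 69%, 4% and 7% across the four columns.

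**Step 4: sensitivity.** Screening on the unadjusted barrier-adherence correlation gives 1.36 instead of 1.47 at the reference effects with n = 28. Stronger effects than the plan's reference values (d = 1.2, ρ = 0.6, p<0.05) bring inflation down to 1.12 at n = 28 and 1.03 at n = 40.

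**Step 5: what the bias comes from.** Without the screen the estimate averages the truth in every cell, so the whole inflation comes from selection. A stricter screen makes it larger. If the promised multiplicity adjustment governed the screen, it would limit false positives but increase the overstatement in whatever survives.

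**The case against.** The best defence is that Aim 3 is labelled exploratory, sits apart from the primary outcome, and belongs to a 40-person pilot. That stands, and it limits the severity. It does not remove the point, because exploratory estimates are more useful when they are complete and unselected, and because Hypothesis 3 is worded as a prediction for all the domains.

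Three stronger readings are tempting and should not be made.

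- **A fixed inflation factor.** A reader might infer that the plan itself implies something like 1.2- to 5-fold. It does not, since neither the threshold nor the true path sizes are given. The 5-fold end comes from a cell in which only about 4% of trials would pass.
- **Documented use of the indirect effects in the next trial.** The sentence "These analyses will support the clinical interpretability of effect sizes in adherence change for future studies" might be taken that way. It directly follows the plan to relate adherence change to symptoms and quality of life, and precedes the mediator step. The Power section confirms that clinical outcomes are meant. It is no evidence about how the indirect effects will be used.
- **Screened-out barriers vanish.** They do not. The first stage of Aim 3 gives them both path analyses, and the Aim 2 text models the barriers longitudinally. What they lack is a planned indirect effect with its interval.

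**Conclusion.** The point holds in a limited form. The plan states a rule that selects on both components of the quantity it then estimates in the same patients, so the reported indirect effects are biased away from zero. Bootstrap standard errors computed after selection do not repair the point estimate.

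The direction follows from the rule, while the size depends on assumptions. Under a p<0.05 screen it is about 1.5-fold (28 patients) and 1.2-fold (40 patients) at the plan's reference effects, and about 4- to 5-fold for small true paths. Over the same effects, a p<0.20 screen gives about 1.1 to 3 and a 0.05/6 screen about 1.5 to 8. All of this assumes normal errors, no direct effect and one mediator at a time. The matter is modest in severity and worth correcting because correction is cheap.

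**What to change.** Drop the screen. Pre-specify the single-mediator indirect effect, with its bootstrap interval, for every barrier scale in Table 2: Oxford knowledge, patient-provider interaction, habit index, bipolar routines, chemical use and rule breaking. Add the parent-communication measure or measures already collected (Conflict Behavior Questionnaire, and the parent communication subscale of the attachment inventory). Table 2 places these under developmental mechanisms, and without them Hypothesis 3 is only partly covered.

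Name the multiplicity method and apply it to that full set. Report every estimate, since highlighting only those whose interval excludes zero would bring the same selection back at the reporting stage.

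Treat any multiple-mediator model as exploratory. Choose its mediators from the pre-listed domains and not from screen survivors, and state that it will be unstable with 28 to 40 patients.

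The cost is seven or eight single-mediator fits and wider adjusted intervals, with no new data, visits or participants. If the screen must stay, the minimum is to state its threshold, disclose the selection beside each estimate and repeat the screen inside the bootstrap. That makes the selection visible but does not by itself remove the bias in the point estimate.

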As a reference, for the projected sample size of 40 subjects with up to 30% attrition, given two-sided Type I error of 0.05, two-sample t-tests will have power of 0.70 for effect sizes of at least 0.975. Tests for non-zero correlation will have power of 0.70 for correlations with magnitude of at least 0.438. Note that we are associating change in adherence with change in clinical outcomes, to better calibrate clinical significance in adherence effect sizes related to the target population for future studies.

Confidentiality of Data

To maintain the confidentiality of the data, a unique study identifier to code individual's identifiable data and will store the master list separate from the study data. The key will be stored in a password protected document that only the study staff will have access to. When the study is closed with the IRB (after primary outcomes data has been analyzed), we will delete the file that contains identifiable information and will be securely shred any paper documents containing identifiable information. Electronic data will be stored in CWRU Redcap, CWRU Box, and UH Secure Network Drive. University Hospital PHI will only be stored on the UH Secure Network not on CWRU REDCap or CWRU Box. Paper research data and documents will be stored in a double-locked secure environment in the PI's research offices in the Psychiatry Department at the W.O. Walker Center.

Data Sharing Plan

The deidentified transcriptions will be shared with the study personnel at UC, CCHMC, and UF. The UC site will also send deidentified quantitative data from Phase 3 to CWRU for analysis. Deidentified qualitative and quantitative data will be shared via CWRU Box or email.

The ability for research communities to share data as soon as it is available adds to the ability for discovery to translate into useable innovation and adds value to the research. Therefore, we will adhere to the NIH Grants Policy on Availability of Research Results: Publications, Intellectual Property Rights, and Sharing Biomedical Research Resources. Sharing of data generated by the RCT portion of this project (Phase 3) will be carried out in several different ways. In addition to the report we will submit to NIMH, we intend to make emerging results available both to the community of scientists interested in understanding our research, but especially to those in the community who can use these behavioral techniques to possibly assist their patients.

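### The auxiliary-covariate screen (r >0.40 twice, with no absolute value) is narrower than the plan's own condition for validity under missing at random

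*Combined protocol and SAP*

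**What the plan says.** The Missing Data section states that the proposed models "provide valid analysis as long as auxiliary covariates associated with missingness (if any) are included in the analysis model". That condition has no size threshold and does not mention the outcome. The section then describes a 0/1 indicator of a missing outcome and gives the rule for admitting a covariate as an auxiliary: "If a covariate is correlated with missingness at r >0.40 and is correlated at r >0.40 with the original response variable". Both parts must be met, and neither carries an absolute value. By contrast, the Power section does refer to magnitude: "Tests for non-zero correlation will have power of 0.70 for correlations with magnitude of at least 0.438".

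Three other parts of the document bear on this:

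- **Data Analysis, attrition.** Forty patients are randomised 20:20, and "we expect up to 30% of participants will discontinue study participation during the 24-week study period".
- **Data Analysis, primary model.** Site is the only covariate the plan commits to. Age, gender, SES, comorbidity, mood state, symptom ratings and family history are candidates only.
- **Treatment Randomization.** Allocation is stratified by site and by age (13-17 v 18-21), but the age stratum is not fixed in the model.

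The Missing Data section also plans pattern mixture models, and possibly selection models, to examine the MAR assumption.

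**The concern.** The section sets a condition and then a rule that does not meet it. A covariate can be clearly associated with missingness and still be left out, either because its sample correlation is at or below 0.40 or because it has the wrong sign.

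The sign matters because the adherence outcome is scored so that higher is worse. Suppose lower SES went with both dropout and more missed doses. Both correlations would be negative, and a programmer following the text would exclude SES. A covariate with one positive and one negative correlation fails under either coding direction.

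At stake is whether the primary mixed model contains the variables that make MAR plausible, in a trial that allows for up to 30% attrition. The choice would also rest on noisy correlations from about 40 patients, so the content of the primary model would depend on the data.

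**Working it through.** **1. Inputs.** From Data Analysis: 40 patients and up to 30% discontinuing, so 0.30 × 40 = 12 missing and 28 observed. From Missing Data: the two 0.40 cutoffs. Assumed, because the documents give no values: true covariate correlations of 0.2 to 0.6, and a within-person TRQ correlation ρ of 0.4 to 0.6.

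**2. The plan's own figures.** The Power section gives 0.70 for an effect size of 0.975 and for a correlation of 0.438.

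- t-test with 28/2 = 14 per arm: noncentrality 0.975 × √(14/2) = 2.58, df 26, power 0.6997. This agrees.
- Correlation with n = 28: noncentrality 0.438/√(1 − 0.438²) × √28 = 2.58, power 0.699 treating the covariate as fixed. This agrees. Fisher's z gives 0.651, and bivariate-normal simulation gives 0.666.

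The plan's figures therefore rest on 28 analysed patients. The 0.40 cutoff has no stated derivation to reproduce.

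**3. What r = 0.40 with missingness requires.** The gap between dropouts and completers, in within-group SDs, is r/√(p(1 − p)(1 − r²)).

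- 30% missing: 0.40/√(0.21 × 0.84) = 0.95 SD
- 20% missing: 0.40/√(0.16 × 0.84) = 1.09 SD
- 10% missing: 0.40/√(0.09 × 0.84) = 1.45 SD

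For a 50/50 binary covariate at 30% missing, the difference in dropout rates is 0.40 × √(0.21/0.25) = 0.37, or about 48% v 12%. The two-sided 5% critical r at n = 40 is 0.312. Covariates with 0.312 < |r| ≤ 0.40 are thus significantly associated with missingness but excluded.

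**4. Chance of passing both cutoffs.** Simulation of 60,000 runs per row: normal covariate and outcome, 12 of 40 missing by a latent normal threshold, and the outcome correlation taken from the 28 observed patients.

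| True r with missingness / outcome | As written | With absolute r |
|---|---|---|
| 0.2 / 0.2 | 1% | 1% |
| 0.3 / 0.3 | 6% | 6% |
| 0.4 / 0.4 | 22% | 22% |
| 0.5 / 0.5 | 52% | 52% |
| 0.6 / 0.6 | 79% | 79% |
| −0.5 / −0.5 | 0% | 52% |
| −0.5 / +0.5 | 0% | 52% |

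**5. Bias in an arm mean from omitting one 0.4/0.4 covariate, 30% missing.**

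- Completers only: 0.4 × 0.4 × √(0.30/0.70) = 0.105 SD.
- With baseline TRQ in the model, multiply by (1 − ρ): 0.105 × 0.6 = 0.063 and 0.105 × 0.4 = 0.042 SD.
- With baseline, week 8 and week 12 TRQ, multiply by (1 − ρ)/(1 + 2ρ): 0.105 × 0.6/1.8 = 0.035 and 0.105 × 0.4/2.2 = 0.019 SD.

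These assume that the covariate correlates 0.4 with TRQ at every visit, that visits are equally correlated and, in the last case, that dropout follows week 12. A large-sample simulation gives matching ranges (0.04 to 0.06 and 0.02 to 0.04).

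**6. Bias in the treatment contrast.** If the covariate drives dropout in the same way in both arms, the two shifts cancel. If it acts in one arm only, the contrast shifts by about 0.02 to 0.06 SD. If it acts in opposite directions, the shift is 2 × 0.019 = 0.04 to 2 × 0.063 = 0.13 SD. For scale, the standard error of a difference with 14 per arm is √(2/14) = 0.38 SD, and the reference effect is 0.975 SD.

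**The case against.** The strongest defence is that the screen is only one way into the model. The Data Analysis section already names SES, age and symptom ratings as candidate covariates. The mixed model uses earlier TRQ values, which carry part of what an omitted covariate would carry. Departures from MAR are to be probed by pattern mixture models. Requiring a link to the outcome is also sound, because a covariate related to missingness but not to the outcome causes no bias when omitted. The missing absolute value looks like loose notation, since for a covariate with two negative correlations the signed rule would depend on arbitrary coding. The auxiliary-variable rule also carries a literature citation.

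Most of this stands, and it limits the size of the problem. It does not remove it. Only site is committed to the primary model. Earlier TRQ values reduce the bias but not to zero. Pattern mixture models do not supply covariates left out of the primary analysis. The text as written still differs from the sentence that it is meant to implement.

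A reader might infer that the rule would discard most of the covariates MAR needs. The documents do not support that. They report no covariate correlations, and the pass rate runs from 1% to 79% over the values assumed above. Nor do they show that a signed rule was intended.

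**Conclusion.** The point holds as a minor inconsistency that is cheap to correct. The screen is narrower than the plan's stated condition. It is hard to pass with 40 patients (about 22% for a covariate whose true correlations sit at the threshold on both), and read literally it shuts out negative correlates.

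The expected harm is small: about 0.02 to 0.06 SD in an arm mean at 0.4/0.4 with earlier TRQ modelled. The treatment-by-time comparison is affected only where dropout differs by arm. These sizes rest on 30% missing, which is the top of the plan's range, and on the assumed correlations in the working.

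It would be tempting to conclude that the primary analysis is seriously biased by dropout. The documents do not support that either. The completer-mean figure of 0.105 SD ignores the repeated outcome, and nothing in the documents indicates dropout that differs by arm.

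**What to change.** In Data Analysis, pre-specify a short set of baseline variables that are always in the primary model: baseline TRQ (as part of the repeated outcome or as a covariate), site, the age stratum used in randomisation, baseline HAM-D and SES. The last two move from candidate to fixed.

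In Missing Data, write |r| for both correlations in any further auxiliary screen, and reword the validity sentence and the screen so that they agree. For example, the condition could refer to covariates related to both missingness and outcome, with the fixed set as the main provision and the screen as a supplement.

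This changes analysis wording only. No data collection changes, since all these variables are already recorded. The cost is a few degrees of freedom in a 40-patient model, and the need to define in advance the form in which SES enters.

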For the primary intent-to-treat analysis in Aim 2, we will use longitudinal mixed-effects modeling to evaluate the treatment-by-time interaction of adherence levels between CAE-AYA and ETAU. Significant interaction would indicate that the treatments (i.e., CAE-AYA vs. ETAU) have different trajectories of adherence. We will adjust for site and consider covariates such as age, gender, SES, psychiatric comorbidity (e.g. ADHD), mood state (e.g. (hypo) manic vs. euthymic vs. depressed) and symptom ratings (e.g. HAM-D and YMRS scores), and/or family history. We will consider representing scores as binary outcomes, indicating whether or not an adherence threshold has been met (e.g., 80% adherent), particularly if adherence levels are highly skewed. We will thus consider generalized linear mixed models for binary outcomes (SAS PROC GLIMMIX). Adherence barriers, symptom rating scales and HRQoL scores will also be modeled by through longitudinal mixed models. In addition, we will compare corresponding TRQ and SimpleMed pillbox adherence levels. Correlation between the measures will be estimated and Bland-Altman plots will be generated⁸².

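### The power of 0.70 stated for correlations of 0.438 is about 0.67 at 28 completers, because both variables are observed change scores

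*Combined protocol and SAP*

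**What the plan says.** The Power section sets its terms as "for the projected sample size of 40 subjects with up to 30% attrition, given two-sided Type I error of 0.05". The Data Analysis section gives the source of the attrition rate: "we expect up to 30% of participants will discontinue study participation during the 24-week study period". On these terms the Power section offers two figures for reference. The first is power of 0.70 for a two-sample t-test at an effect size of 0.975. The second is "Tests for non-zero correlation will have power of 0.70 for correlations with magnitude of at least 0.438".

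The next sentence identifies the variables being correlated: "Note that we are associating change in adherence with change in clinical outcomes". The Aim 3 paragraph of Data Analysis describes the same analysis: "we will also examine whether improvements in adherence behaviors correlate with improvements in symptoms and HRQoL". In both places each variable is a change score measured on the participant.

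**The concern.** Power for a test of zero correlation depends on whether the predictor is fixed by design or is itself sampled. With two equal arms, the spread of the predictor is known in advance. With two change scores it varies from sample to sample, and at small sample sizes average power is lower than the fixed-predictor formula gives. The stated 0.438 looked like a fixed-predictor value attached to a correlation between two random variables.

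The stake is limited. This is the only correlation power figure in the plan. A reader judging a null correlation between adherence change and symptom or quality-of-life change would credit the trial with slightly more sensitivity than it has at the stated worst-case attrition.

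**Working it through.** **Inputs, all from the Power and Data Analysis sections.** 40 randomised, 20 per arm; up to 30% attrition, so 40 × 0.70 = 28 completers, 14 per arm; two-sided alpha 0.05; r = 0.438; effect size d = 0.975; stated power 0.70. The critical t value on 26 degrees of freedom is 2.056.

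**Step 1. Confirm the sample size behind the figures.** For the t-test with 14 per arm, the noncentrality is d × √(14/2) = 0.975 × √7 = 2.580. Power from the noncentral t on 26 degrees of freedom is 0.6997, so the stated 0.70 reproduces and 28 is the number used.

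**Step 2. Reproduce the stated correlation figure.** With a fixed predictor, the noncentrality is √n × r/√(1 − r²) = √28 × 0.438/√(1 − 0.1918) = 5.292 × 0.4872 = 2.578. Power is 0.699, again matching the stated 0.70. The two figures are in effect one calculation: converting the effect size to a point-biserial correlation gives r = d/√(d² + 4) = 0.975/√4.9506 = 0.438.

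**Step 3. Recompute for two observed variables.** Under bivariate normality, √n in the noncentrality is replaced by the square root of a chi-square variable on n − 1 = 27 degrees of freedom, and the noncentral t power is averaged over that distribution. At r = 0.438 and n = 28 this gives 0.667. A simulation of 400,000 trials gives 0.666. The plain Fisher z approximation, √25 × atanh(0.438) = 2.349 against 1.96, gives 0.651.

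**Step 4. Solve for the correlation that gives 0.70.** At n = 28 under the Step 3 model, r = 0.4525, or about 0.453. The difference from the stated value is 0.453 − 0.438 = 0.015.

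**Step 5. Sensitivity to attrition (r = 0.438, bivariate normal).**

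| Completers | Attrition | Power |
|---|---|---|
| 28 | 30% | 0.667 |
| 29 | 27.5% | 0.684 |
| 30 | 25% | 0.699 |
| 36 | 10% | 0.782 |
| 40 | 0% | 0.825 |

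**Step 6. Sensitivity to the distribution.** The Aim 2 analysis text allows for a binary version of the outcome, "particularly if adherence levels are highly skewed", so normality cannot be taken for granted. With a linear model, normal errors and 28 completers, simulation (200,000 runs each) gives power of 0.68 for a uniform predictor and 0.63 for an exponential one. Both are below 0.70.

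**The case against.** The strongest reply is that the stated figure is correct under a recognised convention. Aim 3 regresses adherence change on barrier change and says the symptom and quality-of-life associations will be examined in like fashion. Regression inference conditions on the predictor, so a fixed-predictor power calculation is defensible. The replacement also needs bivariate normality, which the plan itself has reason to doubt.

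Part of this stands. There is no arithmetic error, and the test is valid under either view. But power at the planning stage has to average over a predictor spread not yet seen, and the plan describes tests of correlation between two measured changes. The non-normal cases tried move the answer within 0.63 to 0.68, not up to 0.70. Doubt about normality is a reason to state the assumption, not to keep 0.438.

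A reader might also infer that the plan claims 0.70 power for the barrier tests, which are to be adjusted: "Multiple comparisons adjustment will be applied for barrier variable analyses". The documents do not support that reading. The Power section states its alpha of 0.05 openly and ties the association to clinical outcomes, and the adjustment for barriers is announced separately in Data Analysis. The absence of a disclaimer is not a false claim, and the documents give neither a method nor a number of tests from which to compute adjusted power.

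**Conclusion.** The point holds as a small overstatement. At 28 completers and two-sided 0.05, power for a correlation of 0.438 between two change scores is about 0.67 rather than 0.70, and 0.70 needs about 0.453. This rests on approximate bivariate normality and on the full 30% loss. At 30 or more completers the stated figure holds to rounding or is exceeded. The plan does not say to which visit the changes run; if to one before week 24, more pairs could be available and the gap would shrink.

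Severity is minor. The figure is labelled as a reference, Aim 3 is exploratory, and the sample size of 40 is not derived from it. It would be too strong to call the plan's figure miscalculated: it is a correct fixed-predictor value applied to a setting where neither variable is fixed.

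**What to change.** Replace the correlation sentence in the Power section with wording such as: *With 28 completers and two-sided 0.05, assuming approximate bivariate normality, tests of correlation between two change scores have power 0.70 for |r| of about 0.453 or more (0.67 at 0.438).* If the authors prefer the fixed-predictor figure, they should say that 0.438 is conditional on the predictor.

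The cost is one sentence and a slightly less favourable number. Sample size, analyses and conduct stay as they are.
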